10.4 Randomization Procedures

Participants will be randomized in a 1:1 ratio to the two IVR sequences (IVR A followed by IVR B or IVR B followed by IVR A), stratified by study site. The randomization scheme and procedures will be generated and maintained by the MWRI statistical team that will conduct and coordinate the randomization procedures.

10.5 Blinding and Unblinding

Only the site behavioral team and the participants will be blinded. Clinical site staff will be allowed to know the participant's study assignment. Blinding will be maintained until behavioral assessments have been completed.

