2.2 Description of Placebo IVRs

2.2.1 Placebo IVR A

The OCIS placebo IVR A consists of a flexible lavender silicone scaffold, with an outer diameter of 55 mm and a durometer value of 40A. The ring holds two grey cassettes.

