2.2.2 Placebo IVR B

The OCIS placebo IVR B consists of a flexible lavender silicone scaffold, with an outer diameter of 55 mm and a durometer value of 50A. The ring holds two grey cassettes.

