8.3.3 Adverse Event Relationship to Study Product

Relatedness is an assessment made by a study clinician of whether or not the event is related to the study agent. The relationship categories that will be used for this study are:

- Related: There is a reasonable possibility that the AE may be related to the study agent(s)
- Not Related: There is not a reasonable possibility that the AE is related to the study agent(s)

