10.2 Study Endpoints

Primary endpoints

Acceptability

- Proportion of participants preferring each placebo IVR (A or B).

- Mean rating of overall satisfaction with using each placebo IVR.

Secondary endpoint

Safety

- Proportion of participants with genitourinary Grade 2 or higher Adverse Events deemed related to each study product.

Exploratory endpoints

Participant acceptability, attitudes and experiences

- Participant responses to quantitative (i.e., questionnaires) and qualitative (i.e., IDI) assessments. Multiple dimensions will be explored, including:
 - Past experience with IVRs, if any (e.g., Nuvaring, dapivirine IVR)
 - Insertion/removal techniques
 - Ease of insertion/removal
 - Comfort during use
 - Experience with/awareness of inserted IVR
 - Spontaneous expulsions and voluntary removals
 - Experience of IVR use during vaginal sex or menses
 - Perceived benefits and concerns/challenges with the IVR as a future HIV and/or dual purpose (HIV and pregnancy) prevention option
 - Perceptions of sexual partner(s)

Sexual partner attitudes and experiences

- Sexual partner responses during IDI related to:
 - IVR attributes, including acceptability and preferences
 - Perception of participant's experience using the IVR during the study
 - Physical sensation of the participant's IVR use during sex (as relevant)
 - Perceived benefits and concerns/challenges with the IVR as a future HIV and/or dual purpose (HIV and pregnancy) prevention option

Vaginal microbiota

- Change from baseline in composition of vaginal microbiome following each placebo IVR use.
- Change from baseline in Nugent score following each placebo IVR use.

Social harms and social benefits

- Participant or sexual partner self-report of social harms (i.e., non-clinical adverse consequences of study participation or product use that may manifest in social, psychological, or physical ways).
- Participant or sexual partner self-report of social benefits (e.g., positive consequences of product use disclosure, self-confidence, improved communication with intimate partner) resulting from IVR use and/or study participation.

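### The only secondary safety endpoint depends on a relatedness call by clinicians who may know the ring, and no comparison free of that call is planned

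*Combined protocol and SAP*

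**What the plan says.** The secondary objective (3.2) is to compare the safety of rings A and B. It has one endpoint, in 10.2: "Proportion of participants with genitourinary Grade 2 or higher Adverse Events deemed related to each study product".

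Section 8.3.3 says who decides what counts: "Relatedness is an assessment made by a study clinician of whether or not the event is related to the study agent". There are two categories, and the threshold for the positive one is a matter of judgement: "Related: There is a reasonable possibility that the AE may be related to the study agent(s".

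Section 10.5 describes the masking: "Only the site behavioral team and the participants will be blinded". It continues: "Clinical site staff will be allowed to know the participant's study assignment". No reason is given.

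Section 10.7.3 tabulates the number and percentage of participants with the 10.2 safety endpoint by ring, with exact binomial confidence intervals. It names no test for safety and plans no by-ring table of events irrespective of relatedness. The reviews by the safety review team and the independent safety physician (8.1, 8.2, 10.7.1) are oversight. They are not described as masked, or as re-judging relatedness.

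Section 8.3.1 requires every AE to be documented whatever its severity or presumed relationship to product.

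**The concern.** An event enters the endpoint only after a subjective yes-or-no call, and the person making that call may know which ring is in place. If that knowledge moves the threshold by even a little, the two rings are counted by different rules.

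The crossover gives no protection here. It balances person and order, but a bias tied to the ring follows the ring into both sequences. Masking the participant does not help either, because the participant does not decide relatedness.

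Section 10.1 says that findings across primary, secondary and exploratory endpoints are to inform the design of a future drug-loaded ring. A between-ring safety difference produced by attribution, or a real one hidden by it, would feed into that choice. As planned, no companion figure would let a reader tell these cases apart.

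**Working it through.** **1. The plan's own figure.** Table 8 gives a minimum detectable difference of 0.20-0.25 for adverse events at prevalence 0.10-0.30, with 90% power, two-sided alpha 0.05, 100 participants and 10% loss. A continuity-corrected two-proportion formula with 90 per ring gives 0.20 at prevalence 0.10 and 0.25 at 0.30, so the row reproduces. Masking does not enter that calculation. The issue is what the endpoint measures, not its stated power.

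**2. Mechanism.** Let p be the risk of a genitourinary Grade 2+ event from any cause, set equal on both rings so that there is no true difference. Let r1 and r2 be the shares called related on the two rings.

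- Apparent related-only risks: p x r1 and p x r2
- False difference: p x (r2 - r1)
- False risk ratio: r2 / r1, whatever p is

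Neither p nor r is given in the documents; the values below are assumptions. I took p = 0.20 and 0.30, r1 = 0.50, and r2 = 0.50, 0.60 or 0.70.

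**3. Chance of a significant result.** The test is an exact McNemar test on 90 pairs (the expected completers in 10.3), two-sided 0.05, with the two rings' responses independent within a woman. Writing a = p x r1 and b = p x r2, the discordant-pair probabilities are a(1 - b) and b(1 - a). For p = 0.20, r1 = 0.50 and r2 = 0.70: a = 0.10, b = 0.14, discordant 0.10 x 0.86 = 0.086 and 0.14 x 0.90 = 0.126.

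| p | r1 vs r2 | Apparent risks | False difference | Rejects |
|---|---|---|---|---|
| 0.20 | 0.50 vs 0.50 | 0.10 vs 0.10 | 0 | 2.8% |
| 0.20 | 0.50 vs 0.60 | 0.10 vs 0.12 | 0.02 | 4.4% |
| 0.20 | 0.50 vs 0.70 | 0.10 vs 0.14 | 0.04 | 8.7% |
| 0.30 | 0.50 vs 0.50 | 0.15 vs 0.15 | 0 | 3.0% |
| 0.30 | 0.50 vs 0.60 | 0.15 vs 0.18 | 0.03 | 5.4% |
| 0.30 | 0.50 vs 0.70 | 0.15 vs 0.21 | 0.06 | 12.9% |

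The false risk ratio is 0.60/0.50 = 1.2 or 0.70/0.50 = 1.4.

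**4. Sensitivity to a wider gap.** With 30% vs 70% called related, the false difference is 0.04, 0.08 and 0.12 at p = 0.10, 0.20 and 0.30, and the test rejects in 13%, 34% and 54% of trials. That gap is large, and nothing in the documents points to it.

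**5. Limits of the test.** The plan does not name this test for this comparison. Section 10.7.2 mentions McNemar's test for change from baseline and lists chi-square, logistic or exact methods for comparing rings. Section 10.7.3 gives only tabulation and intervals for safety. The rejection rates therefore gauge how visible the bias would be; they are not the plan's error rate.

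**6. Same inputs, relatedness ignored.** The expected difference is p - p = 0 in every row, provided events are elicited and graded alike on both rings.

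**The case against.** The trial is openly described as partially blinded (4.1, 10.1). The people who give and collect the two primary, self-reported outcomes are masked, so clinician knowledge bears on one secondary endpoint. The documents do not contradict themselves here. All of this stands, and it is why the point asks for an added analysis and not a redesign.

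The illustrated effect is also small. It is 2-6 points against a detectable difference of 20-25 points, and an exact 95% interval on 90 women is about 13 points wide at 9/90 and 18 points wide at 19/90. A mild bias would seldom look convincing. This stands too, but 10.7.3 reports estimates, and estimates are read as such.

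Four stronger readings are tempting and are not supported:

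- **Bias will occur, probably against the firmer ring.** Nothing shows that attribution will differ or which way. Neither ring releases a substance, and one definition of relatedness applies to both.
- **Clinicians could simply be masked because the rings look alike.** The descriptions in 2.2.1 and 2.2.2 differ only in durometer, 40A against 50A. But that is a difference in hardness, which staff may feel at the digital placement check or an assisted insertion or removal (6.2, 7.3.1, 7.3.4). The pouch label is not visible in the text, so it cannot be said whether pouches already carry a code.
- **The participant blind, and so the primary endpoints, is weakened.** The documents do not say that the clinicians who judge relatedness also instruct participants. Section 7.7 separates counselling staff from questionnaire staff when feasible, and 10.5 keeps the blind until behavioral assessments are done.
- **A count regardless of relatedness is free of bias.** Staff who may know the ring still elicit and grade the events, so the Grade 2 cut-off remains open to influence.

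**Conclusion.** The point holds as a gap in the safety analysis. The whole between-ring safety comparison rests on a judgement that may be made with knowledge of the ring, and nothing planned stands beside it that does not depend on that judgement.

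The size cannot be estimated from the documents. With the assumed inputs (equal event risk of 20-30%, 50% vs 60-70% called related, 90 independent pairs) the false difference is 2-6 points, and a significant result arises in about 4-13% of trials against about 3% with equal attribution. If attribution is equal, there is no false difference.

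This is a low-cost improvement to a secondary endpoint. It does not invalidate the design and does not touch the primary endpoints or the Table 8 figures.

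**What to change.** **Main change.** In 10.2 and 10.7.3, pre-specify the proportion of participants with genitourinary Grade 2+ AEs on each ring regardless of relatedness. Compare it within participant, for example as a paired risk difference with a 95% confidence interval among women exposed to both rings, and require it beside the related-only result. Because relatedness would no longer tie an event to a ring, state the rule that does so by date of onset, including events that begin in the 7-21 day gap.

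**Cost.** No new data are needed, since 8.3.1 already requires all AEs to be recorded. The work is one definition, one onset rule and one extra table.

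**Optional.** Where practical, do not disclose the ring code to the clinician who grades and attributes AEs. This would also reduce bias in grading, which the added analysis cannot do. It may be imperfect because of the hardness difference, and it needs coded dispensing and a way to break the code. If the sponsor judges it impractical, a sentence in 10.5 giving the reason would be enough, with the added analysis kept.

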10.6 Participant Accrual, Follow-up and Retention

We anticipate participant accrual to take place over a period of approximately 3-5 months. Each participant enrolled will be followed for a period of approximately 9-11 weeks.

10.7 Data and Safety Monitoring and Analysis

10.7.1 Study Monitoring

No DSMB oversight is planned for this study. The MATRIX Clinical Trials Hub will conduct interim reviews of study progress, including rates of participant accrual, retention, completion of primary and secondary endpoint assessments, and study or laboratory issues. The ISP will conduct interim review of incident AEs. These reviews will take place approximately every 3 months, or as needed. At the time of these reviews, or at any other time, the ISP or PSRT may convene a panel (composed of the ISP, PSRT and protocol statistician[s]) to review study findings. This panel may recommend that the study proceed as designed, proceed with design modifications, or be discontinued. Safety monitoring will be done by the PSRT.

10.7.2 Primary Analysis(es)

All participants randomized into the study who complete Visit 5 will be included in the primary analysis.

When the use of descriptive statistics to assess group characteristics or differences is required, the following methods will be used: for categorical variables, the number and percent in each category; for continuous variables, the mean, median, standard deviation, quartiles and range (minimum, maximum). Overall and within-treatment group assessment of the change from the baseline measurement to a follow-up measurement will be analyzed using McNemar's test (for categorical response variables) or the paired t-test or Wilcoxon signed-ranks test (for continuous variables). When using formal testing to assess endpoint differences between users of Ring A or Ring B, the following methods will be used: for binomial response variables, chi-square tests and

logistic regression (or exact testing methods); for continuous variables, t-tests and linear regression or nonparametric methods if data are non-Normal.

To assess the adequacy of the randomization, participants in each arm will be compared for baseline characteristics including demographics and laboratory measurements using descriptive statistics. Due to the small sample size, formal comparisons will not be done.

We will calculate overall estimates for mean satisfaction rating at Visits 5 and 9 (Likert 10-point scale) to permit comparisons between Ring A and Ring B. We will test for difference in mean overall satisfaction rating (Likert 10-point scale) between Ring A and Ring B using a two-sided t-test (primary endpoint), adjusting for randomization sequence. A nonparametric test will be used if normality assumptions are not met. Analyses will examine sociodemographic and behavioral correlates of acceptability rating (i.e., satisfaction) using linear regression models with robust standard errors. We will calculate the proportion preferring each ring and explore properties and usability characteristics associated with preferences.

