10.3 Sample Size and Power Calculations

MATRIX-003 will enroll approximately 100 participants, with approximately 20 participants per site. Participants will be randomized to the 2 crossover sequences in a 1:1 ratio, allocating 50 women per IVR sequence. In light of the short study duration and the teams' previous experiences conducting similar research with the study's target population, we anticipate 5-10% LTFU. Therefore, we expect approximately 90 participants will complete the study. A subset of up to 30 study participants will complete an IDI after the 2nd period of IVR use. We will enroll up to 30 sexual partners to complete an IDI after the participant completes the 2nd period of IVR use.

Note: Replacement participants will be considered in consultation with study leadership if LTFU is higher than expected (i.e., >10%).

Table 8 presents the range of potential detectable effect sizes reflecting differences in primary and secondary endpoints of the two study products assuming 90% power, two-sided $\alpha=0.05$, varying standard deviations or marginal probabilities, a sample size of 100, and 10% LTFU.

The primary acceptability endpoints will be measured at Visits 5 (satisfaction) and 9 (satisfaction and preference). Secondary endpoints will be assessed cumulatively to calculate an overall proportion experiencing the outcome (e.g., AE). Exploratory acceptability endpoints will be collected at Visits 5 and 9. In addition, interim data on experience using the placebo IVR will be collected 1 and 2 weeks after each ring insertion.

Table 8: Range of potential effect sizes for each endpoint

Continuous outcomes: effect size is difference in means (satisfaction) and difference in proportion (preference)			
Endpoint	Endpoint type	Standard deviation	Minimum detectable difference
Overall satisfaction (Likert scale 1-10)	Primary: Acceptability	4.3-5.75	1.5-2.0
Preference between Ring A and Ring B	Primary: Acceptability	$p_a: 0.40-0.50$	$p_b: 0.23-0.33$
Binary outcomes: effect size is risk difference			
Endpoint	Endpoint type	Prevalence	Minimum detectable difference
Adverse events	Secondary: Safety	0.10 – 0.30	0.20 - 0.25

Qualitative data collection

Participant experiences: Up to 30 study participants will be purposively selected and invited to complete an IDI ideally at or within 1 week of Visit 9 but no later than 3 weeks after Visit 9.

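### Table 8 claims 90% power for a Ring A v Ring B preference gap of 0.17, but a valid test has about 42–53%, and Section 10.7.2 names no test for this primary endpoint

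*Combined protocol and SAP*

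**What the plan says.** Section 10.2 lists as a primary endpoint "Proportion of participants preferring each placebo IVR (A or B"), beside mean satisfaction. Section 10.3 has preference measured once, at Visit 9.

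Table 8 is computed "assuming 90% power", two-sided alpha 0.05, "a sample size of 100, and 10% LTFU". The same section adds that "we expect approximately 90 participants will complete the study". The table describes its upper block as follows: "effect size is difference in means (satisfaction) and difference in proportion (preference"). The row is labelled as preference between Ring A and Ring B. It gives p_a 0.40–0.50 and, as the minimum detectable value, p_b 0.23–0.33. The lead-in presents the table as differences between the two products under varying standard deviations or marginal probabilities. Nothing says that p_a is a null value.

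Section 10.7.2 gives satisfaction a named two-sided t-test adjusted for sequence. For preference it says only: "We will calculate the proportion preferring each ring and explore properties and usability characteristics associated with preferences". Its general rule for formal comparisons between users of Ring A or Ring B reads "for binomial response variables, chi-square tests and" logistic regression, with exact methods as an alternative. McNemar's test appears only for change from baseline.

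**The concern.** Every completer uses both rings and gives one preference. The share preferring A and the share preferring B are therefore two cells of one multinomial sample: a woman counted for A cannot be counted for B. The variance of their difference exceeds that for two independent groups, and far exceeds that for one share against a fixed constant. A sizing that ignores this understates the detectable gap.

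At stake is a primary endpoint meant to inform the design of a drug-loaded ring. A reader of Table 8 would think the trial very likely to detect a split such as 50% v 33%, and could take a non-significant result as evidence that the rings are about equally liked. With no test named, the method could also be chosen after the answers are known.

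**Working it through.** **Inputs.** From Section 10.3: n = 90 (100 enrolled less 10%), two-sided alpha 0.05 (z = 1.960), power 90% (z = 1.2816), and the pairs 0.40/0.23 and 0.50/0.33. The response options are not given, so the share with no preference is an assumption.

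**1. Reproduce Table 8.** One-sample test with p_a as a known null: p_b = p_a − (1.960 + 1.2816) × √(p_a(1 − p_a)/90).
- p_a = 0.40: 0.40 − 3.2415 × 0.05164 = 0.233 (stated 0.23; power at the stated value 90.9%).
- p_a = 0.50: 0.50 − 3.2415 × 0.05270 = 0.329 (stated 0.33; power 89.7%).

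**2. Other routes to the same figures.** Power at 0.40/0.23 and 0.50/0.33 respectively:
- Two independent groups of 90: 69% and 64%.
- Paired proportions, zero correlation: 68% and 63%.
- Paired proportions, correlation +0.5: 92% and 89%.

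Of the routes tried, only the fixed null and the positive correlation come close to 90%.

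**3. The correlation that applies.** For mutually exclusive answers it is −√(p_a p_b / [(1 − p_a)(1 − p_b)]):
- 0.40/0.23: −√(0.092/0.462) = −0.45.
- 0.50/0.33: −√(0.165/0.335) = −0.70.
- Forced choice: −1.

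A positive correlation is impossible here.

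**4. Power of a valid A-v-B test.** Let s = p_a + p_b and d = p_a − p_b. The standard error is √(s/n) under equal preference and √((s − d²)/n) under the alternative, so power ≈ Φ{[d − 1.960√(s/n)] / √((s − d²)/n)}.

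| Pair | s | Calculation | Power | Exact sign test |
|---|---|---|---|---|
| 0.40/0.23 | 0.63 | Φ[(0.17 − 0.1640)/0.0817] | 53% | 48% |
| 0.50/0.33 | 0.83 | Φ[(0.17 − 0.1882)/0.0943] | 42% | 38% |

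The exact column conditions on the number of women stating a preference and averages over that number.

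**5. Gap detectable with 90% power.** Solve d = 1.960√(s/90) + 1.2816√((s − d²)/90).
- Forced choice (s = 1): 0.2066 + 0.1273 = 0.334, about 33% v 67%.
- 10% no preference (s = 0.90): 0.317.
- 37% no preference (s = 0.63, the total in the 0.40/0.23 pair): 0.265.

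**6. What survives in Table 8.** An exact binomial test against 0.5 with 90 answers rejects at 55 v 35 or beyond. Its actual size is 4.5%, and its power is 90.2% when the true share is 0.33. The 0.50/0.33 pair is therefore right as a share of 0.33 against a null of 0.50, which under a forced choice is a 33:67 split. The 0.40/0.23 pair has no such reading, because 0.40 is not equal preference under a forced choice.

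**7. A conditional risk in the analysis text.** Suppose the general rule were read as a two-group chi-square of x/90 against (90 − x)/90. At 52 v 38, z = (14/90)/√(2 × 0.25/90) = 2.09, so that test rejects where the exact test does not. Its type I error is 2[1 − Φ(1.960/√2)] = 16.6% asymptotically and 17.0% by enumeration at n = 90 (11.3% with continuity correction). With a 'no preference' answer, the uncorrected test has 13.6% at true shares 40/40/20 and 10.7% at 33/33/34.

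**The case against.** The strongest reply is that Table 8 reproduces as a one-sample calculation, so the sizing never treated the two shares as independent groups, and the 42–53% comes from reading p_a and p_b as competing shares. The first part is right: two independent groups do not reproduce the row, and nobody should infer that they were assumed. The reply rescues the 0.50 end as a distance from 0.5. It does not rescue the row as printed, which describes a difference in proportions between two products and nowhere calls p_a a null; nor does it explain 0.40.

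A reader might also infer that the plan commits to a two-group chi-square with a 17% false-positive rate. The documents do not support that. The general rule also lists logistic regression and exact methods, does not say two-group, and is not tied to preference. A one-sample chi-square or an exact binomial test fits its wording and has size 4.5% at n = 90. The 17% further requires a forced choice, which the documents do not state. It is a reason to name the test, not a property of the plan.

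Sequence adjustment is not essential for validity. With 45 women per sequence and an assumed 65/35 recency effect, the pooled exact test has size 3.5%.

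**Conclusion.** The preference row of Table 8 is not correct as a statement about the gap between Ring A and Ring B. At the printed splits a valid test has about 42–53% power (38–48% exact) instead of 90%. The gap detectable with 90% power is about 0.33 under a forced choice, or about 0.27–0.32 if 37% to 10% state no preference, against the printed 0.17. These figures assume 90 answers at Visit 9 and one answer per woman; the no-preference range is assumed. The 0.50/0.33 pair stands only as a one-sample comparison of 0.33 with 0.50.

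Section 10.7.2 leaves this powered primary endpoint without a named test, null value, confidence interval or rule for 'no preference'. Alone, that would be missing detail. It matters more here because the sizing and the analysis text do not identify the same comparison.

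**What to change.** - **Table 8.** Restate the preference row as a one-sample test of the share preferring A against 0.5, with a detectable split of about 33:67 from 90 stated preferences. Drop or correct the 0.40/0.23 pair. If 'no preference' is a permitted answer, say so and give the detectable gap for a plausible share of such answers.
- **Section 10.7.2.** State that preference is tested once, by an exact binomial (sign) test against 0.5 among women stating a preference, with an exact confidence interval and the 'no preference' share reported alongside. Make clear that the general rule for users of Ring A or Ring B does not apply to this endpoint. A sequence-stratified version is an optional supplement.

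The cost is one table row and a few sentences. No new data or change in sample size is required. The downside is that the stated detectable A-v-B gap becomes less favourable, roughly double the printed 0.17 under a forced choice (0.33/0.17 ≈ 1.9).
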